- Patients with measurable inoperable, histologically confirmed lung and esophageal carcinomas, thymic neoplasms, germ cell tumors, malignant pleural mesotheliomas or chest wall sarcomas, as well as patients with gastric, colorectal or renal cancers and sarcomas metastatic to the thorax are eligible.
- Patients with favorable germline SNPs in ABCB4, ABCB11, RALBP or CYP8B1 that are associated with resistance to mithramycin-induced hepatotoxicity.
- Patients must have had or refused first-line standard therapy for their malignancies.
- Patients must be 18 years or older with an ECOG performance status of 0–2, without evidence of unstable or decompensated myocardial disease. Patients must have adequate pulmonary reserve evidenced by FEV1 and DLCO equal to or greater than 30% predicted; Oxygen saturation $\geq 92\%$ on room air. ABG will be drawn if clinically indicated.
- Patients must have a platelet count greater than or equal to 100,000, an ANC equal to or greater than 1500 without transfusion or cytokine support, a normal PT/PTT, and adequate hepatic function as evidenced by a total bilirubin of <1.5 X upper limits of normal (ULN) and AST/ALT ≤ 3 X ULN. Serum creatinine within normal institutional limits or creatinine clearance ≥ 60 mL/min/1.73 m² for patients with creatinine levels above institutional normal.

Design:

- Single arm Phase I dose escalation to define pharmacokinetics, toxicities and MTD.

- Patient cohorts will receive 24h infusions of mithramycin targeting total doses previously administered during 7 daily six hour infusions at 30-50 mcg/kg.
- The 24h infusions will be administered every 14 days (1 cycle). Four cycles will constitute one course of therapy.
- Pharmacokinetics and toxicity assessment to define MTD will be assessed during Cycle 1 of the first course of therapy.
- Due to uncertainties regarding potential cumulative toxicities, no intra-patient dose escalation will be allowed.
- Once MTD has been defined, patients will be enrolled into two cohorts (primary thoracic malignancy vs neoplasm of non-thoracic origin metastatic to the chest) to determine clinical response rates at the MTD, using a Simon Optimal Two Stage Design for Phase II Clinical Trials targeting an objective response rate (RECIST) of 30%.
- Following each course of therapy, patients will undergo restaging studies. Patients exhibiting objective response to therapy or stable disease by RECIST criteria will be offered an additional course of therapy.

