1.3.4 Recent Experience with Mithramycin in Adult Oncology Patients at the NCI

1.3.4.1 12C0151 Phase II Trial

In the recent Phase II trial (12C0151) in TSB/CCR/NCI, 12 patients (10 males; 2 females; median age 51y; range 40-72y) with refractory thoracic malignancies (6 MPMs, 2 esophageal cancers, 2 lung cancers, 2 synovial sarcomas) received 6h mithramycin infusions q day x 7, every 28 days. Response rates following two cycles, pharmacokinetics, and systemic toxicities (Cycle 1) were evaluated. A total of 20 cycles were administered to 12 patients; all were evaluable for toxicities. No objective responses were observed in 7 patients who were evaluable for treatment responses. No myelosuppression, uncontrollable nausea or vomiting were observed. No patients experienced bleeding. The lack of these toxicities, which have been associated with mithramycin treatment (66) may be attributable at least in part to higher purity of the current drug relative to what had been used previously.

Eight patients experienced transient, asymptomatic dose-limiting transaminitis following 25 mcg/kg/infusions. This toxicity always occurred on Day 4 of the infusion. Percutaneous biopsies from three individuals revealed apoptotic hepatocellular death (Figure 7A). Four patients (2 with MPM) had no hepatotoxicity and tolerated dose escalation to 30 mcg/kg/infusion. Peak and steady state mithramycin levels were 20 and 8 nM, respectively, which were not different in patients with or without hepatotoxicity (Figure 7B).

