3.1.2 Dose Escalation

3.1.2.1 Dose Escalation for MTD Determination

The doses of mithramycin which will be used at each level are indicated below, and are based on modeling performed using pharmacokinetic results obtained in our recent Phase II mithramycin trial (protocol 12C0151) and of initial patient results in this trial (16C0152). The schema of drug exposure has been selected to optimize growth inhibition and transcriptional reprogramming in clinical settings. The overall goal is to administer a dose of mithramycin during a 24-hour infusion that is equivalent to the total dose administered during 7 daily 6 hour infusions at a dose of 30-50 mcg/kg per infusion (210-350 mcg/kg) used in our recent Phase II trial (12C0151). This dose range would be expected to produce plasma levels approximating 50-100 nM by the end of infusion (**Figure 10**). The selection of only those patients with favorable ABCB4, ABCB11, RALBP and

CYP8B1 genotypes should allow more efficient escalation of mithramycin doses with acceptable toxicities.

**Dose Escalation Schema for 24h Mithramycin Infusions
(For MTD Determination in Initial Cohort 1 Arm 1 Patients)**

Dose Level	Dose (mcg/kg)
-1	30
-1A	45
1	60

The first 3 patients in Cohort 1 received mithramycin and experienced Grade 4 ALT/AST elevations. Two of these three patients continued mithramycin at a reduced dose (30 mcg/kg; DL-1) without exhibiting dose-limiting toxicity (refer to Section 1.3.4.2).

As such in Amendment E of this protocol (Version Date 11/01/2019) the dose levels have been amended and MTD determination will begin anew with 3 patients at dose level DL-1 (30 mcg/kg), to be assessed during the first treatment cycle for DLT. The MTD is the dose level at which no more than 1 of up to 6 patients experience DLT during Cycle 1 of treatment, and the dose below that at which at least 2 (of ≤ 6) patients have DLT.

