Following completion of the fourth cycle of therapy, all patients will undergo evaluation consisting of physical exam, blood work, and appropriate staging studies to define response to treatment. Those individuals who exhibit disease progression will be taken off study. Patients who exhibit stabilization or regression of their disease will be eligible for 4 additional mithramycin infusions at the same dose level at which they were originally treated. Patients will continue therapy in this manner until off-study criteria have been met.

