3.2 DRUG ADMINISTRATION

Given our recent findings within our recent Phase II mithramycin trial (12C0151) pertaining to ABCB4, ABCB11, RALBP and CYP8B1 SNPs that distinguish patients who did and did not experience mithramycin-mediated hepatotoxicity, this protocol will accrue only those patients with favorable ABCB4/ABCB11/RALBP/CYP8B1 genotypes.

Mithramycin will be administered intravenously via central line over 24 hours once every 14 days (+7 days/-3 days). 12 mg IV of dexamethasone will be administered one hour prior to each infusion. Four cycles will constitute one course. Intravenous hydration will be provided as clinically indicated.

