Non-hematological, Grade 3 or 4 (excluding ALT, AST, hemorrhage and QT prolongation)	
 • Apply maximum supportive care recommendations. Hold mithramycin therapy until recovery to Grade ≤ 1 (up to 21 days from start of cycle) and start the next treatment cycle at the next lower dose level. • If recurrence of adverse event after drug hold/interruptions is observed at the reduced dose, and maximum supportive care measures applied, hold drug once again until recovery to Grade ≤ 1 (up to 21 days) and start the next treatment cycle 1 dose level lower. Note: If patient's toxicity recovers to Grade ≤ 1 prior to Day 7 of treatment cycle, dosing for that cycle may resume 1 dose level lower. • If symptoms continue to persist at Grade 3 or 4, following a maximum of 2 dose reductions, discontinue drug.
QT prolongation, Grade 3 or 4	
 • Cardiology consultation will be obtained to determine whether any cardiac functional assessment is warranted or if therapy should be delayed or discontinued. When warranted, ECGs will subsequently be reviewed by the NCI consulting cardiologist. • If therapy is continued, dose reduce 1 level for Grade 4 events.
Bleeding Events (hemorrhage)	

General Adverse Events	Action
Grade 1 events	
 Continue mithramycin therapy at full dose prescribed. Apply maximum supportive care recommendations.
Grade 2 events	
 Apply maximum supportive care recommendations. Hold mithramycin therapy until recovery to Grade \leq 1 (up to 21 days from start of treatment cycle) and start the next treatment cycle at 1 dose level lower. If recurrence of adverse event after drug hold/ interruptions is observed, and maximum supportive care measures applied, hold drug once again until recovery to Grade \leq 1 (up to 21 days from start of treatment cycle) and start the next treatment cycle at 1 additional dose level lower. If symptoms continue to persist at any grade, discontinue drug.
Grade 3 events	
 Discontinue mithramycin
Grade 4 events	
 Discontinue mithramycin

All Grade 2-4 hemorrhage events will initiate full hematologic evaluations as indicated in Section 3.5.1-Coagulation Studies, as well as formal Hematology consult.
	
Hematological Adverse Events	

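### A note in Section 3.3 lets dosing resume within the same cycle, which the schedule of one 24h infusion every 14 days does not allow and the dose table does not define

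*Combined protocol and SAP*

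**What the plan says.** **The action row.** In the Section 3.3 table, the row for Grade 3 or 4 non-hematological events leaves out ALT, AST, hemorrhage and QT events. Its first bullet holds drug until recovery and then says to "start the next treatment cycle at the next lower dose level". Its second bullet deals with an event that comes back at the reduced dose: hold again, then give the next cycle one further level down. The note sits inside that second bullet. If toxicity recovers to Grade 1 or lower "prior to Day 7 of treatment cycle, dosing for that cycle may resume 1 dose level lower".

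**The schedule.** Section 3.2: "Mithramycin will be administered intravenously via central line over 24 hours once every 14 days (+7 days/-3 days", that is, up to 7 days late or 3 days early. The Précis: "The 24h infusions will be administered every 14 days (1 cycle). Four cycles will constitute one course of therapy". Section 3.1.2.1 describes a further course in the same terms: patients "will be eligible for 4 additional mithramycin infusions at the same dose level at which they were originally treated". The Cycle 1 summary in Section 3.1 starts the infusion on Day 1, completes it on Day 2 and starts the second cycle on Day 15. Appendix 2 marks mithramycin on Day 1 only.

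**The dose levels.** Section 3.3 sends every reduction to the table in Section 3.1.2.1, which lists 30 (DL-1), 45 (DL-1A) and 60 mcg/kg (DL1) and nothing lower. The same section reports: "The first 3 patients in Cohort 1 received mithramycin and experienced Grade 4 ALT/AST elevations".

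**The concern.** Once the infusion ends on Day 2, the cycle contains no further dosing. An instruction to *resume* dosing in that cycle must therefore mean a second infusion, which the schedule excludes, or completion of an interrupted one, which the note does not say and the protocol does not define. The note also pulls against its own bullet, which defers dosing to the next cycle.

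The patients concerned have just had a Grade 3 or 4 event related to the drug. Two people following the same row could act differently, and the dose received in that cycle would no longer match the assigned level on which toxicity and pharmacokinetic results are reported. If the note were applied to a Phase I Cycle 1 event, it would also allow further dosing in the same cycle after what is generally a dose-limiting toxicity (DLT).

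**Working it through.** The documents state no cycle total, so there is no figure to reproduce. The check compares timing, instructions and dose.

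**1. Timing (Sections 3.1 and 3.2).**
- Planned next start: Day 1 + 14 = Day 15, as the Cycle 1 summary says.
- Earliest next start: Day 1 + 14 − 3 = Day 12, so starts are at least 11 days apart.
- The note sets its Day 7 limit on recovery and gives no date for dosing. If dosing follows on recovery, it falls on Day 6 at the latest, 6 − 1 = 5 days after the start, against the minimum of 11.

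**2. Instructions side by side (Section 3.3, same row).** Both action bullets defer the reduced dose to the next cycle. Only the note puts it in the current cycle. The Appendix 3 footnote on pharmacokinetic sampling after a dose modification also refers to the next cycle.

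**3. The note read strictly in its bullet (recurrence at a reduced dose).**
- Start at 45: first reduction to 30; on recurrence there is no level below 30. The bullet's own next-cycle reduction meets the same gap.
- Start at 30: there is no level for even the first reduction.
- Start at 60: reduced to 45, then 30 on recurrence, at most 45 + 30 = 75 mcg/kg in the cycle. However, Section 10 counts 6 + 6 + 3 = 15 Phase I patients, with the 3 at DL1 already enrolled, so it counts no new patients at 60.

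At the levels now open, the note points to a dose that does not exist.

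**4. The note applied to a first event.** Let f be the fraction of the first infusion given, and suppose a full dose at the next lower level follows. Cycle total = f × (assigned level) + (next lower level).
- From 45: 45f + 30 exceeds 60 when f > 30/45 = 2/3, or 16 of 24 hours at a constant rate. The maximum, at f = 1, is 75 mcg/kg; 75/60 = 1.25 and 75/45 = 1.67.
- From 60: 60f + 45 exceeds 60 when f > 15/60 = 1/4, with a maximum of 105. No new patients are counted at this level.

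**5. The note read as completing an interrupted infusion.** To show the ambiguity, assume half of a 45 mcg/kg infusion was given (22.5 mcg/kg). One level lower could then mean:
- topping up to the lower level: 22.5 + 7.5 = 30;
- giving the remaining half at the lower level: 22.5 + 15 = 37.5;
- giving a full lower-level dose: 22.5 + 30 = 52.5.

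The protocol does not choose among these and sets no limit on the cycle total.

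**6. DLT rules (Sections 3.1.1 and 3.1.2.1).** A related non-hematological event of Grade 3 or higher in Cycle 1 is a DLT, apart from alopecia and from nausea, vomiting or diarrhea that supportive measures control. Section 3.1.2.1 makes Cycle 2 treatment available to patients without a Cycle 1 DLT. Applied in Cycle 1, the note would allow dosing sooner than that.

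**The case against.** The best defence is that *resume* naturally suggests finishing something interrupted. The Section 3.3 table covers interruptions, and a 24h infusion can be interrupted. Completing it would not breach the 14-day schedule. That softens the conflict, but the note does not limit itself to this case, and the dose remains undefined under it.

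A reader might go further in three ways that the documents do not support.

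- **That the text as written permits 75 mcg/kg, above the level where the first three patients had Grade 4 transaminase elevations.** In its bullet the note applies to a patient already reduced, so a start at 45 cannot lead to 45 + 30 in one cycle. The note's wording does not expressly exclude a first event, which is why the total stands only as a conditional one. The 60 mcg/kg for those patients is itself inferred: the sentence in Section 3.1.2.1 gives no dose, Section 10 places three subjects at DL1, and the table gives DL1 as 60. Section 1.3.4.2, which that paragraph cites, was not in the text reviewed. The row also excludes ALT and AST, so the comparison is of dose only, and two infusions days apart are not shown to be equivalent to one at the summed dose.
- **That the note corrupts the maximum tolerated dose (MTD).** In its bullet it needs an earlier event and a later cycle at a reduced dose, so it cannot arise in Cycle 1. If it were misapplied there, the triggering event would generally already be a DLT at the assigned level, before any second exposure.
- **That the note was carried over from the earlier trial, in which patients "received 6h mithramycin infusions q day x 7, every 28 days".** It would fit such a schedule, but that protocol is not available and the origin cannot be checked.

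**Conclusion.** The point holds as a contradiction in a dosing instruction. The note either conflicts with one infusion per cycle, the 11-day minimum and its own bullet, or it points to a dose that the protocol does not define. This rests on the text alone and is firm.

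The dose consequence is conditional. A cycle total above 60 mcg/kg, at most 75, requires all of the following: the note is applied to a first event at 45 mcg/kg, more than two-thirds of that infusion was given, and a full 30 mcg/kg follows. Bias in the MTD is not shown. The correction is still needed, because the rule governs patients with Grade 3 or 4 drug-related toxicity and cannot be followed consistently as written.

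**What to change.** The sponsor should reconcile the note with its own bullet, the DLT and continuation rules in Sections 3.1.1 and 3.1.2.1, the dose table, Section 3.2 and the Appendix 2 calendar. The amended text should state:

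- which instruction governs, and whether it covers first events, recurrences or both;
- if completing an interrupted infusion is meant, what one level lower means for a partly given dose;
- what applies when the table has no lower level;
- how such a cycle is counted for dose, pharmacokinetics and toxicity.

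Which clinical rule is right is for the sponsor to decide; none is proposed here.

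One statistical safeguard belongs with this. A triggering Cycle 1 event that meets the DLT definition must stay counted at the assigned level. Leaving such patients out of DLT scoring because they were re-exposed could remove true DLTs and push the MTD upward.

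The cost is a sentence or two in an amendment, with no added patients or procedures.

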3.4 CRITERIA FOR ADDITIONAL TREATMENT

Patients will be eligible to continue to receive mithramycin for as long as they do not experience clinical or radiographic disease progression (see Section 6.2) and tolerate mithramycin (as defined in Section 3.3).

Patients may receive the next course of mithramycin at the same dose level (or reduced level as above) provided the following criteria are met by Day 21:

- patient has stable or responding disease;
- has a platelet count $\geq 75,000/\mu\text{L}$ (transfusion independent), and an ANC $\geq 1000/\mu\text{L}$, and
- meets other laboratory parameters defined in the eligibility criteria (Section 2.1); and
- has not met any criteria for removal from treatment or off study (Section 3.6).

3.5 ON STUDY PROTOCOL EVALUATION (APPENDIX 2: STUDY CALENDAR)

3.5.1 Baseline Evaluation

- Complete history and physical examination including assessment of vital signs and ECOG status (within 4 days prior to treatment).
- Laboratory
 - ROUTINE LABS:
 - Complete blood count, differential
 - Chemistries: LDH, SGPT (ALT), SGOT (AST), alkaline phosphatase, bilirubin (total and direct), BUN, creatinine, amylase, lipase, electrolytes, ionized calcium, magnesium, phosphorus, uric acid, albumin and thyroid panel (within one week prior to treatment).
 - Total and fractionated serum bile acid levels (within 2 weeks prior to treatment).
Note: Results need not be back prior to commencing treatment.
 - Coagulation Studies: PT/PTT; lupus anticoagulant (LA) test if indicated (within one week prior to treatment).
 - Urinalysis.
 - Women of child-bearing potential will have a urine or serum βhCG pregnancy test. *Note: this test is to be done within 2 days prior to start of treatment.*
- Radiographic Evaluations (refer to Appendix 2 for details). *Note: Obtain within 4 weeks prior to treatment.*
- Liver elastography assessment by ultrasound (within 2 weeks prior to treatment).
- Research Labs (refer to Appendix 3 for details). *Note: May be obtained at any point within 2 weeks of commencing treatment.*

3.5.2 Monitoring During Treatment

- Physical exam, to include vital signs, weight, toxicity evaluation and ECOG status within 4 days of each treatment cycle.

- Laboratory Evaluations (Days 1-5 while hospitalized, unless otherwise indicated below*):
 - CBC with differential count.
 - Chemistry: sodium, potassium, chloride, CO₂, creatinine, glucose, BUN, albumin, ionized calcium**, magnesium, alkaline phosphatase, ALT/GPT, AST/GOT, total bilirubin, total protein.
 - Total and fractionated serum bile acids on Day 1 (prior to infusion) and Day 5 of Cycle 1 (+/- 3 days) and at treatment evaluation.
 - Coagulation Studies: PT/PTT/Thrombin Time, Fibrinogen.
Note: The patient may have evaluations and lab work obtained through his or her local physician in between treatments and have the results faxed to the Research Nurse. The Research RN will contact the patient as noted above to discuss toxicity.

*** Note:** Day 1 labs can be drawn on the day prior to infusion. In between treatments, the above labs may be drawn twice weekly (+48 hours between labs). For patients not experiencing Grade 3 or 4 toxicities these labs may be drawn once weekly in between treatments per PI discretion instead.

**** Ionized calcium** is not part of a standard lab panel and may be omitted if not available or not covered by insurance when performed outside NIH. 12-Lead EKG:
 - Cycle 1: Days 1 (within 2 hours prior to infusion), 2 (within 2 hours post-infusion), 3, 4 and 5, to evaluate for QT prolongation potential.
Note: EKGs may be done outside of the specified times if unexpected events in clinic prevent staff from conducting the study within the specified timeframe. EKGs performed outside of this window will NOT be considered protocol deviations.
 - Cycle 2 and subsequent cycles: within 2 hours prior to start and within 2 hours following completion of infusion.
- Ultrasonic liver elastography Day 4 of Cycle 1 (+/- 3 days) and Day 1 (+/- 3 days) of subsequent cycles and at treatment evaluation.

3.5.3 Research Evaluations (Refer to [Appendix 3](#), Unless Otherwise Indicated Below)

Note: All samples are to be placed on wet ice and transported to the Thoracic Epigenetics Lab (TEL) within one hour of draw:

- Coagulation Studies.
- Pharmacokinetic (PK) Studies.
- Radiological Evaluations (refer to [Appendix 2](#)).
- Research Labs for PD studies on plasma and PMBC.
- Tumor Biopsies, to be collected as described in Section [5.2](#) (refer to [Appendix 2](#) for details).

Note: *Within 2 days prior to biopsies:* Normal PT/PTT with exception of lupus anticoagulant, platelets $\geq 75,000/\mu\text{L}$, peripheral ANC $\geq 750/\mu\text{L}$.

3.5.4 Follow-up Evaluations

After completion the last treatment cycle (see Section 3.4 for criteria for retreatment), patients will be monitored weekly or more frequently if indicated until all clinically significant toxicities resolve to less than or equal to Grade 1 or baseline as follows:

- Toxicity Evaluation
 - Laboratory evaluation: CBC, Chemistries (Sodium, potassium, chloride, bicarbonate, creatinine, glucose, BUN, albumin, total calcium, ionized calcium*, magnesium, inorganic phosphorus, alkaline phosphatase, ALT/SGPT, AST/SGOT, total bilirubin, direct bilirubin, lactate dehydrogenase, total protein, creatine kinase, uric acid), PT/PTT
- For patients with stable disease or responding to therapy, the following will be done every 2 months until off study criteria are met:
 - History and physical exam
 - Laboratory evaluation: CBC, (Sodium, potassium, chloride, bicarbonate, creatinine, glucose, BUN, albumin, total calcium, ionized calcium*, magnesium, inorganic phosphorus, alkaline phosphatase, ALT/SGPT, AST/SGOT, total bilirubin, direct bilirubin, lactate dehydrogenase, total protein, creatine kinase, uric acid), PT/PTT
 - Radiographic Evaluations (see [Appendix 2](#)).

Note: The patient may have evaluations and lab work obtained through his or her local physician during follow up.

* Ionized calcium is not part of a standard lab panel and could be omitted if not available or not covered by insurance when performed outside NIH.

